Annex D: Evaluation team experience	55

Project title	GenPMTO Evaluation - Pilot study
Developer (Institution)	Implementation Sciences International Inc. (ISII)
Delivery partner (Institution)	Barnardo's
Evaluator (Institution)	Ending Youth Violence Lab (part of the Behavioural Insights Team)
Principal investigator(s)	[name]
Evaluation plan author(s)	[name], [name], [name], [name], [name]
Evaluation setting	3 boroughs in London (Barking & Dagenham, Brent, and Tower Hamlets)
Target group	Caregivers of young people aged 8-14, who have been identified as being at risk of committing violent acts and/or entering into the criminal justice system.
Planned number of participants	 Approximately: 100-120 primary caregivers (quantitative sample) 9 caregivers (qualitative sample) 6 practitioners (qualitative sample) 6 referrers (qualitative sample) 2 Barnardo's managers (qualitative sample)
Funding source and declaration of interests	Funding was received for this work, from the Youth Endowment Fund (YEF) and from philanthropist [name] (via Prism the Gift Fund). There are no known conflicts of interest associated with this publication, and there has been no significant financial support for this work that could have influenced its outcome.
Version history	Note that protocol publication was delayed from December '24 to March '25, as recruitment challenges delayed the start of the study. The protocol has been published prior to randomisation for the first parent cohort (originally expected to occur in December '24/January '25).

1. Study rationale and background

About the Ending Youth Violence Lab

The Ending Youth Violence Lab ('the Lab') was founded in Summer 2022, bringing together expertise in intervention, evaluation and youth violence. It is funded by [name] and the Youth Endowment Fund (YEF) and is being incubated at the Behavioural Insights Team (BIT).

The Lab's mission is to catalyse a step change in understanding and tackling youth violence. To do this, we do 3 things: Firstly, we identify promising interventions which seek to address youth violence. Secondly, we fund the development and delivery of these interventions. Thirdly, we conduct research to assess the delivery of interventions, identify ways to improve them, and explore the potential for further evaluation (with a focus on early-stage testing, to support the work of YEF).

We prioritise three strands of activity:

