Establishing evaluability	Recruitment (study)	 Referrals How many families are referred to the project/study? What factors affect the volume of referrals? Referral suitability How many/what proportion of referred families are eligible? What are the most common reasons for families being deemed ineligible for the project/study? Source of referrals Which agencies and settings are referring families? How many families are being referred by each? Which agencies/settings contribute the most referrals and why? How many referrals are self-referrals (i.e. do not come through intermediaries, but in response to broader promotion/outreach approaches)? Are there differences between referring agencies/settings in terms of what proportion of participants are meeting inclusion criteria? Recruitment and consent How does this vary across referral source and participant characteristics, including: Primary caregiver gender Primary caregiver gender Family SES Given the number of eligible families successfully consented into the evaluation over the time-period of the pilot, would a well-powered RCT be achievable at the efficacy stage over the currently planned time period, or would it need to be extended? What is the typical length of time between referral and randomisation?
	Randomisation	 Feasibility and adherence Is the randomisation approach feasible (i.e. can we randomise straightforwardly as planned in this context, or are there unexpected barriers)? How many/what proportion of recruited participants complete baseline data surveys and are randomised? Is randomisation adhered to (i.e. is randomisation accidentally or intentionally subverted)? How could the approach to randomisation be adapted

to increase feasibility and adherence?
 Acceptability Is randomisation acceptable to families? Is randomisation acceptable to practitioners? Do practitioners feel that evaluation activities (randomisation) impact the quality and ability to deliver the intervention well? In what way? Is randomisation acceptable to Boroughs and referring practitioners? What factors affect acceptability of randomisation? How could the approach to randomisation be adapted to increase acceptability?
 What alternative services or support (specifically parenting support) do the control group receive, if any? To what extent are alternative services similar to GenPMTO?

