The quantitative monitoring criteria used to monitor evaluability-related objectives are described in Table 2 below. While the criteria below offer guidance for the progression of the evaluation on the basis of quantitative assessments, these will also be complemented by qualitative measures, such as ongoing practitioner feedback and interviews with practitioners and caregivers. Overall, we will not establish a deterministic rule about how many green-, amber-, and red-rated criteria would justify/prohibit progression, but instead will use the criteria to support a balanced judgement, weighting the importance of each criteria in the round.

The monitoring criteria specified below were developed iteratively in consultation with both Barnardo's and ISII, and help to ensure that the study does not progress from one phase to the next without sufficient evidence of success.

Table 2. Monitoring and success criteria for pilot study

Research objective	Criterion	Description	RAG scores
Evaluability	Eligible referral volume	Number of months (out of 7 recruitment months) where at least one Borough achieves a 'critical mass' of 30 eligible referrals where we can initiate the study onboarding and randomisation process for a cohort of parents/caregivers. ¹⁷ (OR a critical mass of 30 eligible referrals is achieved across all 3 Boroughs combined, provided those participants have indicated that they are content with online delivery).	Green: 5-6 months Amber: 3-4 months Red: 0-2 months
	Baseline data collection and randomisation	Number of participants who are randomised (and meet the requirements to be randomised, i.e. they're eligible, they've consented, they have complete referral information, and they complete baseline surveys).	Green: 92+ participants (over 2/3rds of 138 target) Amber: 47-92 (up to 2/3rds of target) Red: 0-46 (up to 1/3rd of 138 target)
	Evaluation retention - treatment	Proportion of participants randomised to the treatment group who submit the post-intervention survey. These thresholds are based on the EIF evidence standards guidelines .	Green: 90-100% of participants randomised to treatment Amber: 35-89% Red: <35%
	Evaluation retention - control	Proportion of participants randomised to the control group who submit the post-intervention survey.	Green: 90-100% of participants randomised to control Amber: 35-89% Red: <35%
Outcomes	Outcomes	Directional change in outcome variables for treatment and control.	Green: At least one outcome

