$$Y_{i} = \alpha + \beta_{1} * Treatment + \beta_{2} * Control vector + \varepsilon_{i}$$

In addition to the primary analysis of short- and medium-term outcomes, we will also:

- Conduct sub-group analyses to analyse differential evaluation recruitment and retention, and programme take-up and completion. The characteristics we examine will be pre-specified in the full statistical analysis plan.
- Enable long-term follow-up of offending data. We will collect the necessary data and submit this for archiving and linking according to YEF processes. Given the age of the children in this sample, and the appropriate time to analyse offending data likely being 4+ years after programme completion, this follow-up will be conducted outside of this project. This follow-up analysis may be conducted by the Lab, or by another organisation such as YEF, or commissioned by YEF.

Risks to study validity

Note that while the following risks are not problematic for the pilot per se (in terms of successfully assessing evaluability), they are risks for the overall impact evaluation if the project proceeds to the stage 4 efficacy trial.

Achieving insufficient statistical power

Although not a risk to internal validity per se, there is a risk that we do not acquire sufficient referrals to achieve half the sample size required for a fully powered trial, during this pilot study. This would reduce our ability to detect the impact of GenPMTO overall (once stage 4 is completed), even if there was an effect (i.e. a false negative).

We are aiming to acquire referrals and randomise in 6 (or more) tranches for the pilot study, triggering the onboarding and start-up process when we acquire 30 eligible referrals each month. If we do not reach 30 eligible referrals in each month, we will either need to: i) make the decision to initiate a group in that month with fewer participants than planned - and to compensate for this by committing to run additional cohorts as part of the pilot, or ii) delay the schedule to allow more time for referrals.

As well as limited referrals, study attrition may also impact our ability to achieve sufficient statistical power. This is discussed below.

Attrition (control and treatment group drop-out)

Attrition from the study may reduce the statistical power of our study and introduce bias. Some degree of attrition is to be expected. We will attempt to minimise the impact of this by:

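### The Table 2 randomisation criterion is a cumulative count with no assessment window, so longer recruitment alone can turn it Green, and the value 92 sits in two bands

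*Protocol*

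**What the plan says.** Table 2 of the protocol (Section 4, Monitoring and success criteria) has two recruitment rows.

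- **Eligible referral volume** is time-bound: "Number of months (out of 7 recruitment months) where at least one Borough achieves a 'critical mass' of 30 eligible referrals". Green is 5-6 months, Amber 3-4, Red 0-2.
- **Baseline data collection and randomisation** is a count: "Number of participants who are randomised (and meet the requirements to be randomised". Its bands are "Green: 92+ participants (over 2/3rds of 138 target"), "Amber: 47-92 (up to 2/3rds of target") and "Red: 0-46 (up to 1/3rd of 138 target"). No period is given.

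The footnote to the referral row derives the 138. It plans 7 tranches, one a month from December 2024 to June 2025, with 30 eligible referrals each (210 in all), about 20 randomised per tranche, and at most 15% attrition.

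In Section 5, under the risk of insufficient statistical power, a month short of 30 referrals may be handled by starting a smaller group and "committing to run additional cohorts as part of the pilot, or ii) delay the schedule to allow more time for referrals". Neither remedy has an upper limit.

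Table 1 (Section 3) asks, from the number consented during the pilot, "would a well-powered RCT be achievable at the efficacy stage over the currently planned time period", or whether that period would need extending. The version history records that "recruitment challenges delayed the start of the study".

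**The concern.** A count against a target means something only over a stated period. Here the target came from a monthly plan, but the row dropped the month. Elsewhere the protocol lets recruitment run on when it is slow. With that remedy in use, the row partly measures how long recruitment lasted, and its rating no longer separates a fast pilot from a slow one.

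The ratings inform the recommendation on Stage 4, which is planned as a further 9-12 months of delivery to obtain the second half of the sample. Whether that is feasible depends on the rate. A Green reached only by extension would be read as support for progression although the rate behind it had been Amber or Red in the planned period. Since the start has already slipped because of recruitment, an extended pilot is a realistic case.

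Separately, a count of exactly 92 has two ratings as printed.

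**Working it through.** **Inputs.** 138 randomised, 210 eligible referrals, 7 monthly tranches and 15% attrition (footnote in Table 2). Bands at 46 and 92 (Table 2). Stage 4 of 9-12 months, with the pilot supplying half of 200-240 (Section 5, Sample size). Constant recruitment rates of one half and one third of plan are assumptions chosen for illustration.

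**The plan's own figures.**
- 138/7 = 19.7 per month, against about 20 stated.
- 138 × 0.85 = 117.3 completers, against 120 stated.
- 138/3 = 46 and 138 × 2/3 = 92, both exact. So 92 is not over two thirds of 138; it is two thirds.

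**What the row shows at a slower, constant rate.**

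| Rate | Per month | Count at month 7 | Rating at month 7 | Months to reach 92 |
|---|---|---|---|---|
| Plan | 19.7 | 138 | Green | 92/19.71 = 4.7 |
| Half of plan | 9.86 | 69 | Amber | 92/9.86 = 9.3 |
| One third of plan | 46/7 = 6.57 | 46 | Red | 92/6.57 = 14.0 |

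If Green needs 93, the last two become 93/9.86 = 9.4 and 93/6.57 = 14.2 months. The rating improves with no change in rate.

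**What the time-bound referral row would show.** Planned conversion is 138/210 = 0.657.
- Half rate: 9.86/0.657 = 15 referrals a month, 105 in 7 months. 105/30 gives 3 full tranches, so Amber at best.
- One-third rate: 10 a month, 70 in 7 months, 2 full tranches, so Red.

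When the shortage lies in referrals, that row catches it. It does not catch a shortage after referral. Suppose 5 of 7 months reach 30 referrals (Green) but conversion is half of plan, 0.329. Those 5 tranches randomise 150 × 0.329 = 49. Each added tranche of 30 brings 9.86. Two replacement tranches give 49.3 + 19.7 = 69 (Amber), and five give 49.3 + 49.3 = 98.6 (Green). The plan does not say how many may be added.

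**What the same rate implies for Stage 4.** This treats the 9-12 months of delivery as recruitment time, which is generous because the programme itself takes 14 weeks.
- Half rate: 9 × 9.86 = 89 to 12 × 9.86 = 118 randomised; × 0.85 gives 75 to 101 completers, against 100-120 for the second half.
- One-third rate: 59 to 79 randomised; × 0.85 gives 50 to 67 completers.
- If a half-rate pilot stopped at 92 (92 × 0.85 = 78 completers), the two stages together would give about 154 to 179, against 200-240.

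**The case against.** The strongest reply is that the row is not used alone.

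- The referral row directly above is limited to 7 months and would rate the half-rate case Amber at best.
- Ratings are made monthly, so an Amber or Red at month 7 would be on record before any later Green.
- Section 4 disclaims a fixed rule and calls for a balanced judgement, and the Sample size section promises new power analyses before Stage 4.
- The 138 carries an implied period through its footnote and the 7-month recruitment period in the timeline (Section 11).
- The row's own labels, over and up to two thirds, place 92 in Amber.

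Much of this stands. A reader might infer that the achievability question in Table 1 will be answered wrongly. The protocol does not support that. The question is posed separately, with its own time periods, and extension is one of its stated answers; nothing says it is read off this row. Nor does the half-rate case show that Stage 4 must fail: at 12 months its upper figure, 100.5 completers, just reaches the lower target of 100.

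Three things remain. The referral row does not measure consent, baseline completion and randomisation, and no other row does. The implied period is weak protection, because the dated window began in December 2024 while the protocol, published in March '25, says the first cohort was not yet randomised. And a balanced judgement still needs each rating to have one meaning.

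**Conclusion.** The point holds in a limited form. As written, the randomisation row can move from Amber to Green at half the planned rate by running about 2.3 months beyond the planned 7, and from Red to Green at one third of the rate by running about 7 months beyond. It can thus mislead the Stage 4 judgement on the step from eligible referral to randomisation. It does not decide that judgement, nor the Table 1 question. The overlap at 92 is a small, separate error affecting a single value.

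The sizes assume a constant rate. The referral comparison at half and one-third rates assumes the planned conversion and cumulative filling of tranches. The Stage 4 figures assume 15% attrition and a second half of 100-120 completers. The protocol gives no maximum extension, so the 9- and 14-month cases illustrate what is permitted and do not forecast it.

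**What to change.** 1. Score the row on families randomised within the 7 recruitment months that the referral row already uses, counted from the opening of recruitment. Starting the clock at the first tranche would leave out earlier recruitment delay. State the opening date, because the timeline describes November '24 to June '25 as 7 months.
2. Print the count bands as Green 93+, Amber 47-92, Red 0-46, which follows the row's own labels.
3. Equivalently at month 7, express the row as families randomised per recruitment month with contiguous bands: Green more than 92/7 (13.1), Amber more than 46/7 (6.6) up to and including 92/7, Red 46/7 or fewer. Keep the fractions as the limits so that rounding leaves no gap.
4. State that families from added or delayed cohorts count towards the sample but not towards this rating, and say whether added or delayed months count within the 7 of the referral row.

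The cost is a few words in Table 2 and no new data. The downside is that the pilot cannot improve this rating by running longer.

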¹⁷ We are intending to conduct 7 tranches of randomisation and run 7 GenPMTO groups, one each month between December 2024 and June 2025. Based on conversion rates identified in the previous study stages, we anticipate that each tranche will require 30 eligible referrals (210 across all tranches), which we anticipate will result in approximately 20 participants completing baseline surveys and being randomised (138 across all tranches). We aim for no more than 15% attrition, with 17 completing post-test surveys (achieving our target of 120 completed pre- and post-test outcome surveys across the 7 cohorts). To run an in-person GenPMTO group, we will require 30 eligible referrals within one Borough. To run an online GenPMTO group, we will only require 30 eligible referrals combined across all 3 Boroughs (given that proximity to a physical location will not be an important factor for online delivery). However, these 30 participants need to indicate that their preference is to receive the programme online (or indicate that they have no preference).

		Where null results are those where 95% confidence intervals (CI) include 0, and positive/negative results are those where 95% CIs are entirely above or below 0 (depending on how the variable is coded and which direction is considered an improvement to the outcome).	measure indicates positive results, and none indicate negative results Amber: Null or mixed results Red: At least one outcome measure indicates negative results and no positive results
Deliverability	Programme completion	Proportion of participants randomised to GenPMTO who complete a sufficient proportion of the intervention (defined by developers as attending at least 8 sessions). We will monitor programme take-up and continued attendance throughout the study to identify if we are on track to meet these targets. Note that we will attempt to retain all randomised families in the evaluation, regardless of their attendance.	Green: 80-100% of participants randomised to GenPMTO Amber: 50-79% Red: <50%
	Fidelity	The proportion of practitioners achieving an aggregate mean Fidelity of Implementation Rating System (FIMP) score of at least 4, as rated by ISII programme experts. A FIMP score of 4 is considered to be the lowest score for what is considered acceptable implementation fidelity.	Green: 80-100% of practitioners Amber: 60-79% Red: <60%

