- 1. Designing interview questions to minimise harm and maximise comfort: The Lab will maximise wellbeing and minimise harm during surveys and interviews by (i) structuring questions to build in complexity and difficulty to increase comfort as rapport to develop, (ii) depersonalising questions to elicit comfort and stronger answers (e.g. instead of 'what do you hate about X', ask 'If you had a magic wand, what 3 things would you change about X?"), (iii) being aware of tension discomfort or distress during the interview, repeating that the interview can be stopped may help participants and repeatedly ask if they want to continue, (iv) ensuring that researchers are aware of places to signpost participants and offer this information, and (v) auditing the questions for their sensitivity within the context before the interview.
- Allowing the participants to choose their environment for participating: Where possible the Lab will allow the interviewees to make decisions about the survey and interview setting(s)
 at their home, a public place or over the phone, enabled by the online conference format.
- 3. **Reminding participants of anonymity and data security**: The Lab will seek to minimise anxiety for caregivers by reminding them that the process is fully anonymous and that all identifiable information will be removed from the transcripts and report.

10. Risks

Risk	Impact	Likelihood	Mitigation
Low participation in research activities by caregivers (including differential attrition and higher drop-out from the control group)	High	Medium	 Providing incentives to the control and treatment groups (£20 per completed survey); Ensuring that evaluation activities are designed to be low-impact in terms of burden and time (including offering flexibility in terms of how surveys are completed); Where needed, utilising the relationships that Barnardo's and referring practitioners have built with participants to facilitate access and cooperation. We will inform participants with sufficient notice
			 about planned survey activities. In particular we will attempt to maintain contact throughout the trial period particularly with control group participants, to remind them of their participation in the study and upcoming opportunities to receive their vouchers. We will monitor rates of attrition, and whether there are differences in rates of attrition based on parent/caregiver ethnicity, gender, age, and

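### Three cut-offs in Table 2 conflict with the protocol's own planning figures, and its tranche and decision dates no longer match the stated start of randomisation

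*Protocol*

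**What the plan says.** All three cut-offs are in Section 4, Table 2.

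- **Retention, by arm.** Treatment: "Green: 90-100% of participants randomised to treatment Amber: 35-89% Red: <35" per cent. Control: "Green: 90-100% of participants randomised to control Amber: 35-89% Red: <35" per cent. The treatment row attributes the thresholds to an external evidence-standards guideline.
- **Attrition aim.** Footnote 17, attached to the same table: "We aim for no more than 15% attrition". It gives about 20 randomised and 17 completing post-test per tranche, and 138 randomised and 120 completed overall.
- **Number randomised.** "Green: 92+ participants (over 2/3rds of 138 target) Amber: 47-92 (up to 2/3rds of target"), with Red at 0-46.
- **Referral volume.** The criterion counts months out of seven recruitment months. Its bands are "Green: 5-6 months Amber: 3-4 months Red: 0-2 months".
- **Use of the ratings.** Section 4 applies them monthly. Amber prompts a review or adjustment of delivery and Red a pause. The ratings also inform the Stage 4 recommendation, as part of an overall judgement without a fixed counting rule.
- **Dates.** Footnote 17 plans seven tranches, "one each month between December 2024 and June 2025". Section 11 uses the same months and puts the progression decision in October 2025. The version history in the summary table says publication slipped from December 2024 to March 2025, and adds: "The protocol has been published prior to randomisation for the first parent cohort".

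**The concern.** A traffic-light table works only if each possible result has one colour and the planned result has the colour that means on track. Here the planned retention is Amber, the full count of referral months has no colour, and one value of the randomisation count has two.

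The retention row matters most. If the pilot performs as planned, the monthly monitoring would call for review or adjustment, and the funder would see Amber on two evaluability criteria that the plan itself regards as met.

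The dates matter for another reason. A progression decision tied to a calendar that has already slipped could be taken before the later cohorts have post-test data.

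**Working it through.** **Inputs.** From footnote 17: 138 randomised, 120 completers, 20 randomised and 17 completing per tranche, 7 tranches, at most 15% attrition. From Table 2: the printed bands. From Section 11: the cohort months and the decision date. From the version history: publication in March 2025, before the first randomisation.

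**Reproducing the plan's figures.** 1/3 × 138 = 46 and 2/3 × 138 = 92, which are the printed cut-offs. 120 × 1.15 = 138. 7 × 17 = 119 and 138 × 0.85 = 117.3, both close to 120. The planning figures agree with each other to within rounding.

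**Retention.**
- Planned retention is 17/20 = 85.0%, or 120/138 = 87.0%. Both fall in Amber (35-89%).
- Green needs 0.90 × 138 = 124.2 completers, more than the target of 120.
- Assume 138/2 = 69 per arm and independent losses. Since 62/69 = 89.9% and 63/69 = 91.3%, Green needs at least 63 completers in an arm.

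| True retention | One arm Green, P(X ≥ 63) | Both arms Green (squared) |
|---|---|---|
| 85% | 0.09 | 0.008 |
| 87% | 0.19 | 0.04 |

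If 89.9% were rounded up to 90%, the requirement would be 62. At 85% the probabilities become 0.17 for one arm and 0.03 for both, so the conclusion does not depend on rounding.

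**Number randomised.**

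| Randomised | Rating |
|---|---|
| 46 | Red |
| 47 | Amber |
| 91 | Amber |
| 92 | Green and Amber |
| 93 | Green |

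The Green label says more than two thirds and the Amber label says up to two thirds. By the labels, 92 belongs in Amber; by the printed number, it is also in Green.

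**Referral months.** 0-2 is Red, 3-4 Amber and 5-6 Green. Seven is in no band, although seven tranches are planned in footnote 17, in the randomisation section and in Section 11. The section on risks to study validity speaks of six or more tranches, so the bands may have been written for six. The document does not say so.

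**Dates.** In Section 11 post-test falls three months after baseline: cohort 1 December to March, cohort 7 June to September. If cohort 1 starts in March 2025 and cohorts stay monthly, cohort 7 has baseline in September and post-test in December 2025. That is two months after the planned decision.

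**The case against.** **The guideline as source.** The retention thresholds are said to come from an external guideline, and an evidence-standard threshold can legitimately be stricter than a planning allowance for attrition. That is fair, and it is why keeping 90% is one of the two remedies. It does not explain why an aim that cannot rate Green sits in a footnote to the same table. The guideline cannot be checked here.

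**Small slips, soft rule.** The 92 overlap affects a single value, the missing seventh month is easily read as Green, and no fixed rule links ratings to progression. All of this stands and limits the consequences. The monthly ratings still carry stated actions, so the edges should be unambiguous.

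**The delay is disclosed.** The version history explains it, Section 11 labels its dates as targets, and the risk section allows the schedule to slip. The dates are therefore out of step rather than concealed. December 2025 assumes a March first cohort and monthly spacing.

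**Stronger readings that the protocol does not support.**
- *That Amber starting at 35% retention contradicts a target.* The band is wide, but no stated target conflicts with it.
- *That a large gap between arms goes unnoticed.* Section 10 names this risk ("including differential attrition and higher drop-out from the control group"), and Table 2 has no between-arm row. But any gap above 10 points already puts at least one arm below 90%, so it is not Green.
- *That Green can be reached below a required minimum of 100 completers.* No such minimum is stated. The 100-120 figure is for families recruited, and the only completer target is 120.
- *That a shortfall would carry through to a weaker Stage 4.* The sample-size section plans to re-estimate the Stage 4 sample from pilot data and change recruitment targets.
- *That the delay puts Green on referrals out of reach.* That row counts months reaching 30 eligible referrals, not months in which a tranche is randomised, and recruitment was dated from November 2024.

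**Conclusion.** The point holds for three cut-offs and the dates.

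1. Retention that meets the plan's aim (85-87%) rates Amber. With 69 per arm, independent losses and true retention of 85%, both arms rate Green about 1 time in 100. This is a genuine conflict within the document.
2. A count of 92 randomised has two ratings.
3. Seven of seven referral months has no rating.
4. The tranche and decision dates do not fit the stated publication date. On a March 2025 start with monthly cohorts, the last post-test falls about two months after the decision.

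Items 2 and 3 are drafting errors at the edge of a band. The effect on progression is modest, because the ratings feed a balanced judgement. The changes are still worth making, since these are the pilot's stated success criteria.

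**What to change.** - **Retention.** Choose one and state it in both places: (a) Green at 85% or more per arm and Amber from 35% to below 85%; or (b) keep the guideline-based 90% and restate the attrition aim in footnote 17 as no more than 10%. Leave Red as it is. Under (a), an arm with true retention exactly at 85% still rates Green only about half the time (P(X ≥ 59 of 69) = 0.54), so the rating should be read with its count. Under (b), 120 completers would need 120/0.90 = 133.3, so 134 randomised, which is within the 138 planned.
- **Number randomised.** Green 93 or more, Amber 47-92, Red 0-46. This follows the two-thirds labels already printed.
- **Referral months.** Green 5-7, Amber 3-4, Red 0-2.
- **Dates.** Re-date footnote 17 and Section 11 from the actual first cohort, and place the progression decision after the last cohort's post-test.

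**Cost.** Edits to Table 2, footnote 17 and Section 11. Option (a) loosens Green for retention slightly; option (b) commits the team to a stricter attrition aim. The decision date moves later, to December 2025 or after on a March start.
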